7.7.2. Secondary Endpoints

Multiplicity of study endpoints will be adjusted for using a hierarchical strategy whereby endpoints in the study are only considered to be statistically significant if both of the following are true: 1) p < 0.05 AND 2) the preceding endpoint was found to be statistically significant at the significance level $\alpha = 0.05$. More specifically, the hierarchical order for evaluation of efficacy endpoints is the following: MDS-NMS Total Score (primary endpoint); the combined measure of MDS-UPDRS Parts I, II and III (secondary endpoint), MDS-UPDRS part II (secondary endpoint); Overall CGI-I (secondary endpoint); MDS-UPDRS part III (secondary endpoint); PDQ-39SI (secondary endpoint). Note that all the secondary endpoints have an *a priori* direction, thus one-tailed tests will be utilized for analyses. Only participants who have baseline data collected for the secondary endpoints will be included in these efficacy analyses.

7.7.2.1. Combined measure of MDS-UPDRS Parts I, II, and III (sum score)

This endpoint will evaluate the change in the combined measure of MDS-UPDRS Parts I, II and III at the end of the treatment period (day 112 and 113), which is defined based on the change relative to baseline (days 28/29) scores to provide a measure of global function in PD. This outcome will support that TNM[™] Device treatment provide clinically meaningful changes for people with PD. Changes meeting or exceeding the previously established MCID for this measure (-6.7 points for clinical improvement) (Makkos, Kovacs et al. 2018) will be considered clinically meaningful. MDS-UPDRS Part II.

This endpoint will evaluate the change in MDS-UPDRS part II score at the end of the treatment period (day 112) relative to baseline (mean of day 0 and day 28) scores. Changes will be considered to be clinically meaningful if the mean difference (if normal distribution) or median difference (if non-normal distribution) meets or exceeds the previously established MCID (-3.05 for clinical improvement) (Horvath, Aschermann et al. 2017).

7.7.2.2. Overall CGI-I

This endpoint will evaluate the CGI-I score at the end of the treatment period (day 113) which is defined based on change relative to baseline evaluation at day 29. This CGI-I provides a clinician's determination of overall change as it relates to all aspects of PD. For ease of interpretation, the CGI-I score will be converted using the following formula: Converted CGI-I = 4 - CGI-I. Thus a 0 corresponds to no change, higher magnitude positive values correspond to greater improvements and higher magnitude negative scores correspond to increased worsening. To allow for an effect of site, treatment differences will be modeled utilizing the MMRM with no effect for visit as described previously. If the active treatment arm demonstrates converted CGI-I scores that are statistically significantly greater than those in the passive treatment arm, these results would further support the clinical meaningfulness of change due to tvCVS.

7.7.2.3. MDS-UPDRS Part III

This endpoint will evaluate the change in MDS-UPDRS Part III score at the end of the treatment period (day 113) relative to the baseline (day 29) score. Changes will be considered to be clinically meaningful if the mean/median difference meets or exceeds the previously established MCID (-3.25 for clinical improvement) for this scale (Horvath, Aschermann et al. 2015).

This analysis will be derived only from the ON-state MDS-UPDRS Part III: motor exam scores, and MDS-UPDRS Part III data collected in the OFF-state will not be included in any analysis. The scores will be provided by blinded central raters when available except for scores from item 3 (related to rigidity). Scores for items related to rigidity will be derived from the blinded local rater scores when calculating the MDS-UPDRS part III score. Additionally, the ability of the centralized raters to provide scores will depend on the availability of quality video feed captured by the clinical sites. Video will be captured by Machine Medicine's Kelvin-PD software which was selected by the Sponsor to minimize the risk of video capture that is of inadequate quality for accurate centralized rating. However, it is possible that some video data may be missing or of poor quality, and thus, cannot be rated by a central rater. In cases where MDS-UPDRS Part III data from central raters from either the baseline or the end of treatment visit cannot be scored by the central rater, scores provided by the local raters will be utilized for both the baseline and end of treatment assessments. In cases where the last assessment was captured remotely using telemedicine platforms, the score will be prorated to the scale of the in-clinic MDS-UPDRS Part III. Additionally, the day 0 baseline measure (virtual visit) will be prorated to the scale of the in-clinic MDS-UPDRS Part III will be substituted for the baseline value. This will only occur if a virtual visit is required due to the participant's inability to travel to the site for the end of treatment visit.

* Some motor examinations will be rated by multiple raters to establish inter-rater reliability and approve central raters. Analysis of efficacy should only be performed for the rater assigned by the Sponsor for a given participant or assessment. Additionally, some raters may wish to go back and re-rate an examination. In cases where one rater has performed multiple scores, the most recent score should be utilized in the analysis of efficacy and all prior ratings should be ignored.

7.7.2.4. PDQ-39SI

This endpoint will evaluate the change in PDQ-39SI score at the end of the treatment period (day 112) relative to baseline (mean of day 0 and day 28) scores. The PDQ-39SI is derived by the sum of the eight PDQ-39 scale scores divided by eight (the number of scales), which yields a score between 0 and 100 (with a score of 100 indicating more health problems) (Jenkinson, Fitzpatrick et al. 1997). This is equivalent to expressing the sum of all 39 item responses as a percentage score. Changes will be considered to be clinically meaningful if the mean/median difference meets or exceeds the previously

established MCID (-4.72 for clinical improvement) for this scale (Horvath, Aschermann et al. 2017).

7.8. SAFETY ANALYSIS

7.8.1. Adverse Events (AEs)

Participants will be assessed for AEs every two weeks at minimum (either at study visits or during phone calls). For each group, the AEs will be summarized with frequency and percentage by preferred (PT) term, with all participants in that treatment group as the denominator. Classification will utilize MedDRA System Organ Class (SOC) based on MedDRA® Version 26.0 or other terminology/classification common to Parkinson's disease (e.g., falls, freezing of gait, etc.). AE incidence will be summarized by both severity and causal relationship to Device treatment (as determined by the blinded Principal Investigator or designated study personnel). AEs deemed to be of "possible" or "probable" relationship or "related" to the Device will also be considered as device related. AEs that occurred during the baseline period and post randomization will also be summarized. Additionally, the number of events and number of device-related events per person will be reported as a distribution.

The AE summary tables will provide an overall summary of AEs including the number and percentage of participants who experienced any AE, any SAE, any ADE, any SADE, any UADE, and any discontinuations in study participation due to an AE. Differences between the two arms for each AE type will be evaluated by a Fisher's exact test.

7.8.2. Safety Endpoint

The change in the mini-BESTest between the end of treatment (day 113 or early withdrawal) and the baseline (day 29) will serve as an additional safety endpoint to confirm that TNM[™] treatment does not negatively impact balance, functional mobility and gait in people with PD. Mini-BESTest data collected in the OFF-state will not be included in any analysis .The largest amount by which the median change scores in the passive treatment arm can be better than the median change scores in the active treatment arm is 4 points (Godi, Franchignoni et al. 2013). Two-sided, 95% confidence intervals for the median difference in the Mini-BESTest scores for the two treatment groups will be constructed (Ganju and Rom 2017). If the confidence interval of the difference (active – passive) contains -4, then the no clinically meaningful difference between the groups exists.

7.9. EXPLORATORY ANALYSES

These exploratory endpoints have been added to support clinical applicability of the primary and secondary endpoints. They have been selected to provide additional details that will impact decisions made by prescribing physicians and reimbursement entities. Mean or median change with corresponding 95% confidence intervals and p values will be provided. No adjustments will be made to address a multiplicity of endpoints. Only participants who have

baseline data collected for the exploratory endpoints will be included in these efficacy analyses.

Only participants who have baseline data collected for the exploratory endpoints will be included in these efficacy analyses.

- 1. The Montreal Cognitive Assessment (MoCA): This endpoint will evaluate the change in MoCA score at the end of the treatment period (day 113) relative to the baseline (day 29). The MoCA collected at the study screen will be used to evaluate study eligibility only and will not be included in the analysis.
- 2. The Oral Symbol Digit Modality Test (oSDMT): This endpoint will evaluate the change in oSDMT score (total correct substitutions) at the end of the treatment period (day 113) relative to the baseline (day 29).
- 3. The Modified Schwab and England Activities of Daily Living Scale (S&E): This endpoint will evaluate the change in S&E score at the end of the treatment period (day 113) relative to the baseline (day 29).
- 4. The Parkinson's Disease Sleep Scale-2 (PDSS-2): This endpoint will evaluate the change in PDSS-2 score at the end of the treatment period (day 112) relative to the baseline (day 28).
- 5. The Epworth Sleepiness Scale (ESS): This endpoint will evaluate the change in ESS score at the end of the treatment period (day 112) relative to the baseline (day 28).
- 6. The Functional Assessment of Chronic Illness Therapy-Fatigue Scale (FACIT-F): This endpoint will evaluate the change in FACIT-F score at the end of the treatment period (day 112) relative to the baseline (day 28).
- 7. The Geriatric Depression Scale (GDS): This endpoint will evaluate the change in GDS score at the end of the treatment period (day 112) relative to the baseline (day 28).
- 8. The Parkinson's Anxiety Scale (PAS): This endpoint will evaluate the change in PAS score at the end of the treatment period (day 112) relative to the baseline (day 28).
- 9. The Patient Reported Outcome Parkinson's Disease (PRO-PD): This endpoint will evaluate the change in the PRO-PD score at the end of the treatment period (day 113) relative to the baseline (day 29). The PRO-PD collected at the study screen will be used as a practice-only and will not be included in the analysis as the scale's author indicated that scores from the first completion of the assessment typically have high variability relative to the scores from subsequent administrations. However, in cases where the PRO-PD was collected at the study screen will be used for the baseline measure.
- 10. The MDS-NMS Non-Motor Fluctuations (NMF) Total Score: This endpoint will evaluate the change in NMF score at the end of the treatment period (day 113) relative to the baseline (day 29).
- 11. The Hoehn & Yahr score: This endpoint will evaluate the change in H&Y score at the end of the treatment period (day 113) relative to the baseline (day 29).
- 12. Zarit Burden Interview (ZBI): This endpoint will evaluate the change in ZBI score at the end of the treatment period (day 113) relative to the baseline (day 29).
- 13. The Unified Parkinson's Disease Rating Scale Part I (UPDRS I) This endpoint will evaluate the change in UPDRS I score at the end of the treatment period (day 113) relative to the baseline (day 29).
- 14. EncephaLogTM Finger Tapping Test This endpoint will evaluate the change in the number of total finger tap (left and right hands combined) at the end of the treatment period (day 112)

relative to the baseline (mean of data collected prior to randomization).

- 15. EncephaLog[™] 3 meter Timed Up and Go Test (3m TUG) 3m TUG at home in the clinic: This endpoint will evaluate the change in the duration of the 3m TUG at the end of the treatment period (day 112) relative to the baseline (mean of data collected weekly prior to randomization).
- 16. EncephaLogTM 10 meter Timed Up and Go Test (10m TUG) This endpoint will evaluate the change in the average of replicate values taken for several measures related to the conduct of the 10m TUG at the end of the treatment period (day 113) relative to the baseline (day 29) including stride length, cadence, rotation time, time to complete.
- 17. The International Parkinson and Movement Disorder Society Unified Parkinson's Disease Rating Scale Part I: Non-Motor Aspects of Experiences of Daily Living (MDS-UPDRS I): This endpoint will evaluate the change in MDS-UPDRS I score at the end of the treatment period (day 113) relative to the baseline (day 29).

Treatment adherence, **TNM**TM Device usability/satisfaction (Device Useability Questionnaire) and itemized answers from UPDRS IV assessment tool will also be reported descriptively. To further explore the effects of treatment on individual NMS, effects of treatment on each of the individual MDS-NMS domains will be evaluated. These domains include the following: (1) Depression, (2) Anxiety, (3) Apathy, (4) Psychosis, (5) Impulse control and related disorders, (6) Cognition, (7) Orthostatic hypotension, (8) Urinary, (9) Sexual, (10) Gastrointestinal, (11) Sleep and wakefulness, (12) Pain, and (13) Other. As this is an exploratory analysis, as opposed to a primary or secondary aim, only subjects that demonstrate burden in the specified domain will be evaluated. In practice, this means that if any subject shows no burden on a given MDS-NMS domain throughout the study, then they will be excluded from this exploratory analysis.

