Randomization will occur only after all scheduled assessments and activities have been completed and normal findings on the ear exam is verified and will occur by selecting an envelope from the randomization package, scanning the bar code to the Device and ensuring that the treatments are loaded. The participant and study partner will be trained on how to use and care for the Device, take it home and commence with twice daily treatments.

Clinician version – not for patient use

Treatment Period: The 12 weeks (84 days +/- 3 days) following the pre-treatment baseline period constitute the treatment period. Participants will self-administer treatments twice daily for the full treatment period up until the scheduled end of treatment visit. Treatment adherence will be recorded by the device.

Study staff will confirm and document that they remain blinded to treatment allocation at the beginning of every study visit after randomization. If a study staff member directly responsible for assessment or safety evaluation becomes unblinded, they will no longer be eligible to complete the delegated study assessments per the protocol for that participant.

Phone contacts: (days 43, 56, 71, 84, 99, 112: +/- 1 day)

Participants will complete interim assessments at weeks 8 (day 56) and 12 (day 84). During phone calls scheduled every 2 weeks, study staff will review concomitant medications, potential adverse events and device treatment adherence and issues with the study participant. Study sites are encouraged to have continuous communication with the study participant and study partner outside of the defined protocol visits, in the manner most accommodating to them, to assist with rapport, retention, and the identification of medication changes or adverse events in real-time.

- Interim assessments (week 8/days 56, 57 and week 12/days 84, 85)
 - i. ePROs (days 56 and 84 +/- 1 day) – to be completed in the on-state
 - PDQ-39
 - MDS-UPDRS Part II
 - Transition Questionnaire (day 56 only)
 - ii. Treatment Virtual visits 1 and 2 (days 57 and 85 +/- 3 days)
 - Concomitant medication and adverse event review
 - MDS-NMS (does not include the NMF subscale)
 - Modified MDS-UPDRS Part III (excluding items related to rigidity and postural reflexes)

Virtual visits will be performed using the site's standard of care telemedicine platform.
- End of treatment visit (week 16/days 112, 113 or early termination)
 - i. ePROs (day 112 +/- 1 day) – to be completed in the on-state
 - PDQ-39

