For the primary comparison of interest (i.e. passive-active group following 12 weeks of treatment), the least-squares mean differences with corresponding 95% confidence intervals and p values will be constructed using the MMRM model discussed previously. However, no regulatory claims will be made in relation to these outcomes. Therefore, no adjustments will be made to address multiplicity of endpoints.

Treatment adherence, the Patient Global Impression of Improvement (PGI-I) and itemized answers from both the TNMTM Useability Questionnaire and the UPDRS IV assessment tool for the passive-active group will be reported descriptively. To further explore the effects of treatment on individual NMS, effects of treatment on each of the individual MDS-NMS domains will be evaluated. These domains include the following: (1) Depression, (2) Anxiety, (3) Apathy, (4) Psychosis, (5) Impulse control and related disorders, (6) Cognition, (7) Orthostatic hypotension, (8) Urinary, (9) Sexual, (10) Gastrointestinal, (11) Sleep and wakefulness, (12) Pain, and (13) Other. Only participants that demonstrate burden in the specified domain will be evaluated. In practice, this means that if any participant shows no burden on a given MDS-NMS domain throughout the study, then they will be excluded from this exploratory analysis.

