7.2. ANALYSIS POPULATIONS

Intent-to-treat Population (ITT): All randomized participants will be included in this population. This is the population that will be used for the primary analysis of efficacy and safety.

Modified Intent to treat (mITT): All eligible randomized participants who have completed at least one treatment with the study device and have completed a post-randomization assessment will be included in the mITT population. This population will be used for a secondary analysis of the primary endpoint and will be used to supplement the findings of the primary analysis.

Per-protocol Population (PP): All eligible randomized participants who (1) demonstrate at least 70% adherence of the randomized expected treatments with the Study Device³, (2) have completed the regularly scheduled end of treatment visit (day 113) (3) have not had changes to medications used to treat motor and/or non-motor symptoms of PD during the baseline or

³ Treatment data including dates and treatment durations are captured by the study device. These data files will be analyzed, and treatments lasting a minimum of 10 minutes will be considered as adherent for a given run based on flow oscillations in the Gossling Pulsatility Index after ~7 minutes of treatment Black, R., Rogers, L., Nicoletto, H., Adkins, H., Laskowitz, D. (2016). "Non-invasive neuromodulation using time-varying caloric vestibular stimulation - *abstract*." Headache **56**(S1)..

RCT, (4) have not had changes to medications that mimic motor and/or non-motor symptoms of PD during the baseline or RCT will be included in the PP population. This population will be used for a secondary analysis of the primary endpoint and will be used to supplement the findings of the primary analysis and key secondary analyses.

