7.7.1. Primary Endpoint

The primary endpoint is the change in MDS-NMS total score at the end of the treatment period (day 113) relative to baseline (mean of day 0 and day 29) scores.

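### RCT domain analyses of the MDS-NMS let post-randomisation scores decide who is included, so a treatment effect on new onset filters the arms differently

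*SAP*

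**What the plan says.** The RCT SAP (Appendix 1 to the OLE SAP) states in 7.9 that "effects of treatment on each of the individual MDS-NMS domains will be evaluated", and lists 13 domains. It then narrows the sample: "As this is an exploratory analysis, as opposed to a primary or secondary aim, only subjects that demonstrate burden in the specified domain will be" analysed. The working definition follows: "if any subject shows no burden on a given MDS-NMS domain throughout the study, then they will be excluded from this exploratory analysis". No time point other than the whole study is attached to burden. The only baseline condition in 7.9 is that baseline data exist.

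Other relevant provisions:

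- Protocol 4.1.1 and the schedule of events place the MDS-NMS at days 0 and 29 before treatment, and at days 57, 85 and 113 after randomisation.
- The primary endpoint in RCT SAP 7.7.1 is measured "relative to baseline (mean of day 0 and day 29) scores".
- For the ITT population (RCT SAP 7.2), "All randomized participants will be included in this population".
- For exploratory endpoints (RCT SAP 7.9), "Mean or median change with corresponding 95% confidence intervals and p values will be provided", without adjustment for multiplicity. RCT SAP 7.1 makes these p values informational and rules out statements of significance.
- RCT SAP 7.10 plans no domain analysis in all randomised participants.

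OLE SAP 7.10 repeats the rule: "if any participant shows no burden on a given MDS-NMS domain throughout the study, then they will be excluded".

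**The concern.** Leaving out people who never had a symptom is a reasonable way to avoid diluting a domain effect. The difficulty is that the rule looks at the whole follow-up. Among participants with no burden at baseline, those who develop the symptom stay in and those who remain free of it are removed. Preventing a symptom is one way the device could work, yet the people in whom it is prevented are the ones taken out.

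If the arms differ in new onset, different shares of each arm are kept, and the comparison is no longer between groups formed by randomisation alone. RCT SAP 7.9 says the exploratory endpoints are there to help prescribers and payers decide. A reader of 13 domain effects with confidence intervals would take them as effects in patients who have the symptom, or in all patients. Under this rule they are neither.

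**Working it through.** The plan gives no figure for the domain analyses, so there is none to reproduce. The check is algebraic. Every numerical input below is an assumption, because the documents give no domain prevalence or onset rates.

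**Formula.** A participant excluded under the rule scores zero at every visit, so their change is exactly 0. Let A and P be the mean changes in the full active and passive arms, and pA and pP the shares included. With complete data and no covariates:

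- all-randomised contrast = A - P
- contrast under the rule = A/pA - P/pP

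Let b be the share with baseline burden, dA and dP the mean changes in that group, eA and eP the onset rates among the rest, and w the mean change when burden appears. Then A = b·dA + (1-b)·eA·w and pA = b + (1-b)·eA, and likewise for passive.

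**Main illustration.** b = 0.5, eA = 0.10, eP = 0.25, w = 6. The nominal effect in those with burden is -2; the contrast realised in simulation in those with baseline burden is -1.78.

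- Included: 0.5 + 0.5 × 0.10 = 55% active; 0.5 + 0.5 × 0.25 = 62.5% passive.
- All randomised: 0.5 × (-1.78) + 0.5 × (0.10 - 0.25) × 6 = -0.89 - 0.45 = -1.34.
- Rule, setting dP = 0: (-0.89 + 0.30)/0.55 - 0.75/0.625 = -1.07 - 1.20 = -2.27. Simulation with gamma-distributed scores gives -2.24 to -2.25, which corresponds to dP of about 0.2 to 0.3.

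**Onset rates reversed** (25% active, 10% passive; baseline-burden contrast -1.75).

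- All randomised: -0.875 + 0.45 = -0.43.
- Rule, with dP = 0: (-0.875 + 0.75)/0.625 - 0.30/0.55 = -0.20 - 0.55 = -0.75 (simulated -0.78). This lies between the two usual targets.

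**Second set of assumptions** (w = 4).

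| b | dA, dP | eA, eP | All randomised | Baseline burden only | Rule |
|---|---|---|---|---|---|
| 0.5 | -4, -4 | 0.1, 0.3 | -0.40 | 0 | -1.12 |
| 0.5 | -6, -4 | 0.1, 0.3 | -1.40 | -2.00 | -2.94 |
| 0.5 | -6, -4 | 0.3, 0.3 | -1.00 | -2.00 | -1.54 |
| 0.3 | -6, -4 | 0.3, 0.1 | -0.04 | -2.00 | +0.60 |
| 0.5 | -4, -4 | 0.3, 0.3 | 0 | 0 | 0 |

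First row in full: A = -2 + 0.2 = -1.8 and P = -2 + 0.6 = -1.4, so -1.8/0.55 + 1.4/0.65 = -3.27 + 2.15 = -1.12. The effect is 0 in those with baseline burden and (0.1 - 0.3) × 4 = -0.8 in the rest. The result lies outside both, so it is not a weighted average of them. With b between 0.3 and 0.8 and the other inputs unchanged, the rule gives -1.78 to -0.36, against -0.56 to -0.16 in all randomised. The distortion shrinks as baseline prevalence rises.

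The last row is the no-effect case. Simulated with 83 per arm (the completer number in RCT SAP 4) and an assumed SD of 6, the rejection rate is 4.6% at a nominal 5%.

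**OLE.** OLE SAP 7.8.2 compares change over days 29-113 (passive) with change over days 113-197 (active) in the same people. If the study is read as spanning both periods, a participant at zero throughout contributes 0 to each. The rule then divides the whole contrast by one common share p; at p = 0.65 the factor is 1/0.65 = 1.54. The sign cannot change.

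**The case against.** The strongest reply is that the plan has already limited the consequences. The rule is disclosed and tied to exploratory status. P values are informational, and OLE SAP 7.10 rules out regulatory claims. The primary total score is unaffected. Descriptive statistics include the number of participants, so unequal inclusion would show. Because each excluded change is 0, an unadjusted all-randomised arm mean can be recovered approximately as the included mean times the share included. All of this stands and keeps the priority low. It does not make the rule sound: exploratory status is the only reason given, and a baseline criterion would meet the same aim.

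Three stronger readings are tempting, and the documents do not support them.

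- A reader might infer that the domain estimates are biased in any event, or that the rule creates false positives. With no treatment effect on a domain, both arms are filtered alike, the contrast is zero and type I error stays nominal. With equal onset and a real effect, the rule only rescales.
- A reader might infer that the OLE suffers the same unequal filtering. That comparison is within person, so one set of people serves both periods.
- A reader might take the illustrative figures as the expected error. Prevalence, onset rates and onset severity are all assumed, and the direction changes with them.

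**Conclusion.** The point holds for the RCT in conditional form. Inclusion in each domain analysis depends on post-randomisation scores. When treatment affects new onset, the estimate matches neither the effect in all randomised participants nor the effect in those with baseline burden. Under the stated assumptions the main illustration gives about -2.2, against -1.3 and -1.8; other assumptions shrink the gap or reverse the sign. Distortion is greatest where baseline prevalence is low, and small where nearly everyone has burden at baseline.

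In the OLE the rule rescales the contrast and nothing more. Primary and secondary endpoints are not touched. This is a worthwhile clarification rather than a threat to the trial's conclusions.

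**What to change.** **RCT SAP 7.9.** Restrict each domain analysis to participants with a domain score above 0 at day 0 or day 29. Among the rest, report new onset as a proportion by arm. Give the number excluded per domain and arm.

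**OLE SAP 7.10.** Report the result in all passive-active participants alongside the restricted one. Do not select on OLE baseline: OLE SAP 7.4 defines it as the RCT end-of-treatment value (day 113), which is the outcome of the passive period being compared. In a simulation with no treatment or period effect (scores censored at 0, 30-50% at zero at any visit, latent correlation 0.5-0.85, latent SD 8), that selection produced a spurious benefit of -0.6 to -3.2, while the planned rule gave about 0. Selecting on RCT baseline in the OLE gave a smaller bias, +0.1 to +0.6 against active, so it is not a clean substitute.

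**Cost.** One or two sentences in each SAP and a few table rows; no new data.
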